9.0 SAFETY ANALYSES

The summary of AEs will be limited to treatment emergent SAEs, which are defined as any serious adverse event with onset on or after the initiation of treatment or any serious adverse event already present that worsens in intensity following exposure to study treatment.

For each treatment group (control patients, pooled SB623 patients, and each SB623 dose group) and each category of each antibody subgroup variable, the following results will be presented: number and percentage of subjects with at least one SAE and descriptive statistics for the number of SAEs per patient. For each category of each antibody subgroup variable, a two-sided Fisher's Exact Test will be used to test for a difference between treatments (pooled SB623 versus control) in the proportion of patients with at least one SAE. For each treatment group, a two-sided Fisher's Exact Test will also be used to test for a difference between categories of the subgroup variables in the proportion of patients with at least one SAE.

For each antibody subgroup variable, a logistic regression analysis of SAE incidence will be performed. The model will include terms for the antibody subgroup variable, treatment (pooled SB623 or control), and the antibody subgroup variable by treatment interaction. The p-value for each term in the model will be presented. A statistically significant interaction term would indicate that the effect of treatment on SAE occurrence is different between the two categories of the antibody subgroup variable.

For each antibody subgroup variable, a dose response analysis of the incidence of SAEs will be performed using a logistic regression model with terms for the antibody subgroup variable, SB623 dose (as a continuous variable), and the antibody subgroup variable by SB623 dose interaction. The control group will be excluded from these analyses. The p-value for each term in the model will be presented. A statistically significant interaction term would indicate that the effect of dose on SAE occurrence is different between the two categories of the antibody subgroup variable.

1.0 INTRODUCTION

This document details the analysis plan for the analysis of head magnetic resonance imaging (MRI) variables for the study entitled “A Double-Blind, Controlled Phase 2 Study of the Safety and Efficacy of Modified Stem Cells (SB623) in Patients with Chronic Motor Deficit from Traumatic Brain Injury (TBI)”. It describes the proposed efficacy and safety analyses, including planned summary tables and by-subject data listings. This document is a supplement to the main statistical analysis plan (SAP).

2.0 OBJECTIVES

The overall objective of the study is to evaluate the safety and efficacy of SB623 cells stereotactically implanted in the brains of patients with TBI.

The primary objective of this study is to evaluate the clinical efficacy of intracranial administration of SB623 cells.

The objectives of the head MRI statistical analyses are to evaluate the efficacy of intracranial administration of SB623 cells with respect to head MRI variables and to evaluate the effect of intracranial administration of SB623 cells on the primary efficacy endpoint, the change from baseline in the Fugl-Meyer Motor Scale score at Week 24, stratified by the values for various head MRI variables.

3.0 STUDY DESIGN

3.1 Overview

This is a double-blind, sham surgery controlled study of stereotactic, intracranial injection of SB623 cells in patients with fixed motor deficits from TBI. The study will be conducted at approximately 30 sites in North America (i.e., United States), Eastern Europe (i.e., Ukraine), and Asia Pacific (i.e., Japan).

Table 1 in the main SAP lists the procedures to be followed throughout the course of the study. Head MRIs will be obtained at Screening, Baseline, and Days 2, 8, 28, 168, and 336. DTI and DSC imaging will be obtained at Baseline, and Days 28, 168, and 336.

3.2 Method of Assigning Subjects to Treatment

Two groups, Group 1 and Group 2, will receive SB623 and sham surgery, respectively, in a 3:1 randomization scheme. Group 1 will be further randomized in a 1:1:1 ratio to receive either 2.5 million, 5 million, or 10 million SB623 cells. Randomization will be performed via an interactive web/voice response system (IXRS). For subjects in the United States enrolled outside of Japan, the randomization will be stratified by Glasgow Outcome Scale-Extended (GOS-E) score (i.e., scores 3, 4, 5 or 6); for subjects in Japan, the randomization will not be stratified.

3.3 Blinding

This is a double-blind study. The blind will be maintained by strict role definition and procedures as described in the protocol.

3.4 Changes to the Protocol-Specified Analyses

No changes were made to the protocol-specified analyses.

4.0 EFFICACY AND SAFETY ENDPOINTS IN THIS STATISTICAL ANALYSIS PLAN

4.1 Primary Efficacy Endpoint

The primary efficacy endpoint in the study is the change from baseline in the Fugl-Meyer Motor Scale (FMMS) score at Week 24 among all patients.

4.2 Other Efficacy Endpoints

The other efficacy endpoints of interest in this SAP are the head MRI imaging variables.

4.3 Safety Endpoints

The safety endpoints of interest in this SAP are the presence of new pathologies (e.g., hematomas, tumors, other pathologies).

5.0 STATISTICAL CONSIDERATIONS

5.1 General Methodology

The statistical analysis of the data will be performed using SAS[®] version 9.4 or higher. All statistical tests will be performed at the 0.05 significance level.

The head MRI variables will be documented using summary tables and subject data listings. Continuous variables will be summarized using descriptive statistics, specifically the number of observations, mean, median, standard deviation, minimum and maximum. Categorical variables will be summarized by frequencies and percentages. For the most part results will be presented for the four treatment groups separately and the three SB623 dose groups pooled. The three SB623 dose groups will be pooled for all statistical tests comparing SB623 to sham surgery, except where noted otherwise (e.g., dose response analyses).

Data listings will be sorted by treatment group and subject ID. All date fields will be presented in a format of ddmmyyyy (i.e., 01Jan2018) in the listings.

5.2 Adjustments for Covariates

The primary efficacy endpoint, the change from baseline in the Fugl-Meyer Motor Scale (FMMS) score at Week 24, will be analyzed using a mixed model repeated measures (MMRM) analysis with adjustment for the baseline FMMS score and the GOS-E score at screening as continuous covariates.

5.3 Handling of Dropouts and Missing Data

Every effort will be made to minimize the number of dropouts and to document reasons for dropping out.

For FMMS score, the following imputation rules will be followed for missing data:

- a) impute missing individual items at post-baseline visits using the Last-Observation-Carried-forward (LOCF) method.
- b) impute missing individual items at baseline in the following two ways (i. imputed with a score of 0; ii. imputed with the first observed post-baseline value).

If there are no missing individual items for FMMS score at baseline, then the FMMS results will be shown only once, rather than once for each case specified in b) above.

5.4 Multicenter Study

Approximately 52 subjects will be randomized into the study at approximately thirty (30) sites in North America (i.e., United States), Eastern Europe (i.e., Ukraine), and Asia Pacific (i.e., Japan). A maximum of 12 subjects will be enrolled at each Assessment site, and a maximum of 16 subjects will be enrolled or treated at each Surgery or Comprehensive site, respectively.

5.5 Multiple Comparisons / Multiplicity

Multiplicity considerations will not be taken into consideration in the analyses for this Phase 2 study.

5.6 Examination of Subgroups

The primary analyses of the primary efficacy endpoint and the analyses of the head MRI variables will be performed on the following head MRI subgroups of interest:

- Presence of FLAIR lesion at Day 8
- Presence of enhancing lesion at Day 8
- Location of FLAIR lesion at Day 8

For the purposes of this SAP, when a subject has more than one FLAIR lesion, then the location will be based on the largest lesion. It is recognized that these subgroup variables are measured post-treatment, so they may well be affected by the treatment, but there is interest in the relationship between these variables and the primary efficacy endpoint because it may help to explain what is happening biologically.

The dose response analyses of the primary efficacy endpoint and the head MRI variables will be performed for the following head MRI subgroups of interest:

- Presence of FLAIR lesion at Day 8
- Presence of enhancing lesion at Day 8

Pearson-product moment correlations between the change from baseline in each imaging parameter and the primary efficacy endpoint will be calculated for the following baseline subgroups of interest:

- Age at Informed Consent (18-<50 years of age, 50-75 years of age)
- Gender (male, female)
- Time since injury to treatment (time since injury < median time since injury for all subjects, time since injury \geq median time since injury for all subjects)
- Baseline FMMS score (0-50, 51-100)

6.0 ANALYSIS POPULATIONS

6.1 Modified Intent-to-Treat Population

The Intent-to-Treat (ITT) population will include all randomized patients. All efficacy analyses will be conducted on the modified ITT (mITT) population, which is defined as all randomized patients who complete the surgical procedure. Primary efficacy endpoint analyses will be conducted on this population. In analyses based on the mITT population, subjects will be analyzed according to their randomized treatment assignment.

6.2 Per Protocol Population

The Per Protocol (PP) population will include all randomized patients who have no major protocol violations. Major protocol violations will be identified based on blinded data after the study is completed, but before database lock and the unblinding of the treatment group assignments. All efficacy analyses will be repeated on this population. In analyses based on the PP population, subjects will be analyzed according to their randomized treatment assignment. Analyses based on the PP population will be considered secondary analyses of efficacy.

6.3 Safety Population

The Safety population will include all study patients who undergo surgery (implant or sham). The safety analyses will utilize this population. In analyses based on the Safety population, subjects will be analyzed according to the actual treatment received.

7.0 EFFICACY ANALYSES

7.1 Primary Efficacy Endpoint

The primary analyses of the primary efficacy endpoint will be comparisons of the least-squares mean (LSM) change from baseline in the Fugl-Meyer Motor Scale score at Week 24 of SB623 treated subjects (pooling all SB623 doses) to sham surgery control subjects for the head MRI subgroups defined in Section 5.6. A mixed model repeated measures (MMRM) analysis will be performed with terms for treatment (SB623 or sham surgery), visit, the treatment-by-visit interaction, the baseline Fugl-Meyer Motor Scale score, the baseline Fugl-Meyer Motor Scale score-by-visit interaction, the GOS-E score at screening, and the GOS-E score at screening-by-visit interaction. The Restricted Maximum Likelihood Estimation (REML) procedure will be employed using an unstructured covariance matrix. The LSM and its standard error will be presented for the two treatments, together with a 95% confidence interval for the LSM. The difference in LSMs between treatments and corresponding 95% confidence interval will also be presented, as well as the p-value for the test of the null hypothesis that the LSMs are equal for the two treatments. For these analyses, subgroups will only be used for the SB623 doses and not for the control treatment, i.e., although the analyses will be by subgroup, the subgroups will only be for the SB623 doses. All control patients will be used for the analyses. Missing observations will not be imputed.

In addition, the primary efficacy endpoint, the change from baseline in the FMMS score at Week 24 among all patients, will be analyzed to examine dose response for the head MRI subgroups defined in Section 5.6. As for the primary analysis, a mixed model repeated measures (MMRM) analysis will be performed. The model will include terms for visit, the interaction between SB623 dose and an indicator variable for the Week 4 visit, the interaction between SB623 dose and an indicator variable for the Week 12 visit, the interaction between SB623 dose and an indicator variable for the Week 24 visit, the baseline Fugl-Meyer Motor Scale score, the baseline Fugl-Meyer Motor Scale score-by-visit interaction, the GOS-E score at screening, and the GOS-E score at screening-by-visit interaction. The Restricted Maximum Likelihood Estimation (REML) procedure will be employed using an unstructured covariance matrix. Dose will be treated as a continuous variable, and the control treatment will not be included in this analysis. The estimated coefficient for the interaction between SB623 dose and the indicator variable for the Week 24 visit and the p-value from the test of the null hypothesis that the true coefficient for this interaction equals zero will be presented. Descriptive statistics for the primary efficacy endpoint will also be presented by dose group for each head MRI subgroup.

The Pearson product moment correlation between the change from baseline in the FMMS score at Week 24 and the change from baseline in each head MRI variable will be presented by visit for each treatment group (2.5 million SB623 cells, 5 million SB623 cells, 10 million SB623 cells, pooled SB623, and control). The p-value from a two-sided test based on the t-distribution of the null hypothesis that the correlation equals 0 will be presented. This will be done overall and for the baseline subgroups specified in Section 5.6.

Graphs will be presented showing the mean value of the primary efficacy endpoint at each visit among control patients and among the pooled SB623 patients. This will also be done for patients with the presence of a FLAIR lesion at Day 8 and for patients without a FLAIR lesion at Day 8, but not for all patients combined. For the control treatment, the graphs will be done for all control

patients. The graphs will plot the mean changes (\pm standard error) over time. The graphs will also present the p-value at each post-baseline timepoint from a two-sample t-test testing the null hypothesis that the true mean change is equal for the two treatments.

7.2 Other Efficacy Endpoints

For the pooled SB623 versus sham surgery treatment groups, descriptive statistics will be presented by visit for the actual values and the changes from baseline for each head MRI variable. The difference between treatment groups (pooled SB623 - sham surgery) in the mean change from baseline will also be presented. For each head MRI variable, the one-sample t-test will be used to test whether the mean change from baseline equals 0 for each post-baseline time point. The two-sample t-test will be used to test whether the mean changes from baseline are equal for the two treatments (pooled SB623 vs. sham surgery). Analyses will be performed overall and for the head MRI subgroups specified in Section 5.6.

In addition, each head MRI variable will be analyzed to examine dose response. For each head MRI variable and treatment group (2.5 million SB623 cells, 5 million SB623 cells, 10 million SB623 cells, pooled SB623, and control), the one-sample t-test will be used to test whether the mean change from baseline equals 0 for each post-baseline time point. Linear regression analyses with a term for dose will be used to test the null hypothesis that the coefficient of dose equals 0. Dose will be a continuous variable with the control treatment assigned a value of 0. The p-value from the test of the null hypothesis that the coefficient of dose equals 0 will be presented. Analyses will be performed overall and for the head MRI subgroups specified in Section 5.6.

The numbers and percentages of subjects with FLAIR lesion at Day 8 and with enhancing lesion at Day 8 will be presented by treatment group. Descriptive statistics will be presented for maximum diameter of FLAIR lesion at Day 8, and the x, y, and z dimensions of FLAIR lesion at Day 8. The number and percentage of subjects will be presented for each FLAIR lesion location at Day 8.

The actual values and changes from baseline will be summarized by visit and presence of FLAIR lesion at Day 8 subgroup for the FMMS score using descriptive statistics.

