4.0 DESCRIPTION AND JUSTIFICATION OF TREATMENT REGIMEN

4.1 Dosages

All dosages of cells are to be administered stereotactically through one burr-hole craniostomy using 3 needle tracks within and adjacent to the focal area of injured brain tissue using 5 cell deposits per track at varying depths, with 20 μ L per deposit. Concentrations of cell suspensions to be used will vary depending on the total dosage required per patient. See Table 2 below.

Total SB623 Cells/Pt.	Total SB623 Cells/Deposit	Total SB623 Cells/Track	Concentration of SB623 Cells	Total Volume per Deposit, per Track, and Total
2.5×10^6	1.7 X 10 ⁵	8.3 X 10 ⁵	8.3 X 10 ⁶ cells/mL	20 μL, 100 μL, and 300 μL
5.0 X 10 ⁶	3.3 X 10 ⁵	16.5 X 10 ⁵	17 X 10 ⁶ cells/mL	20 μL, 100 μL, and 300 μL
10 X 10 ⁶	6.6 X 10 ⁵	33 X 10 ⁵	33 X 10 ⁶ cells/mL	20 μL, 100 μL, and 300 μL

Table 2Dosages, Volumes and Cell Concentrations

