5-6 mm) within the cerebral motor sites adjacent to the injured region. The target locations will be selected by the site neurosurgeon to be closest to the motor pathway based on the patient's own neuroanatomy. This procedure is to be repeated with 2 other needle tracks with different trajectories, inserted through the same burr-hole craniostomy.

Group 2

Group 2 will receive sham surgery (sedation, stereotactic planning procedure, partial-thickness skull outer table burr hole, scalp suture, but no penetration of inner table or dura mater). This will be done under sedation and local anesthetic. Again the purpose of the sedation is two-fold: to minimize subject discomfort and to prevent any subject recall or awareness of the procedure to preserve subject blinding. The sham surgery procedure will be scripted to mimic as closely as possible the procedure undertaken by Group 1. Subjects in Group 2 will remain in the Operating Room (OR) for the same duration as Group 1.

Post-Surgical

After completion of the procedure, both groups will receive a CT scan and be admitted to a neurosurgical patient ward for 24 hour observation. The patient will be discharged on the first post-operative day unless complications or local standard medical practice require a longer stay. An MRI is to be done on the first post-operative day (Day 2) to ensure there are no significant bleeding risks.

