8.0 SAFETY ANALYSES

The numbers and percentages of subjects with any subdural hematomas and any parenchymal hematomas will be presented by treatment and visit (Days 8, 28, 168, and 336) and by treatment across all visits. Dose response analyses of these two variables will be performed using a logistic regression model with a term for dose as a continuous variable, with the control dose excluded from the analyses. For each treatment, the total numbers of subdural hematomas and parenchymal hematomas across all visits will be presented. Subdural hematoma and parenchymal hematoma volume and status will be summarized by visit using counts and percentages.

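### The exploratory head MRI dose-response regression codes sham as dose 0 with no implant term, so a sham-to-implant difference that is flat across doses biases the dose slope

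*SAP*

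**What the plan says.** SAP Appendix E (head MRI), section 7.2, describes the dose-response test for every head MRI variable: "Linear regression analyses with a term for dose will be used to test the null hypothesis that the coefficient of dose equals 0". On coding it says: "Dose will be a continuous variable with the control treatment assigned a value of 0". On reporting it says: "The p-value from the test of the null hypothesis that the coefficient of dose equals 0 will be presented". It states no implant-versus-sham term and no other covariate. The same section also plans one-sample tests of change from baseline for each dose, for pooled SB623 and for control, and a two-sample t-test of pooled SB623 against sham.

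Two other dose-response analyses in Appendix E treat control differently. Section 7.1, for the Fugl-Meyer Motor Scale (FMMS), says: "Dose will be treated as a continuous variable, and the control treatment will not be included in this analysis". Section 8.0, for hematomas, fits dose as continuous "with the control dose excluded from the analyses".

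On the procedures, Protocol section 6.0 describes sham as "partial-thickness skull outer table burr hole, scalp suture, but no penetration of inner table or dura mater". For the SB623 arms, Protocol section 4.1 says: "All dosages of cells are to be administered stereotactically through one burr-hole craniostomy using 3 needle tracks within and adjacent to the focal area". Table 2 there gives the same volumes for all three doses (20 µL per deposit, 100 µL per track, 300 µL in total), so only the cell concentration differs.

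**The concern.** The four dose values do not lie on one scale. Moving from 0 to 2.5 million adds cells, but it also adds dural opening, three needle tracks and 300 µL of injected fluid. Moving from 2.5 to 5 to 10 million changes only the number of cells. A single linear dose term cannot tell these two kinds of change apart.

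This matters for MRI because the documents themselves treat the procedure as visible on imaging. Protocol section 11.0 keeps descriptions of the skull defect and needle tract out of the blinded MRI reports because they would reveal the treatment. SAP Appendix E section 5.6 accepts that the Day 8 lesion variables may be influenced by treatment. A sham-to-implant difference in at least some MRI variables is therefore plausible. What is at stake is a reported dose p-value that could be read as evidence of graded cell activity when the three dose arms do not differ.

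**Working it through.** **Inputs**

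- Dose values 0, 2.5, 5 and 10 million cells (Appendix E, 7.2).
- Allocation 3:1, then 1:1:1 within SB623 (Appendix E, 3.2), which gives equal numbers at the four dose values. About 52 patients (5.4) means 52/4 = 13 per value.
- Test level 0.05 (5.1), taken as two-sided.
- Step D between sham and every implanted arm: an assumption, since the documents give none. Range used: 0 to 1.5 SD.

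**The plan's own figure.** No power or sample size is given for the MRI dose test. The only stated calculation is for the FMMS comparison: difference 10.0 − 3.0 = 7.0, SD 7.25, 36 + 12 patients. It reproduces: exact power is 80.9% against the stated 80%, and 48 × 1.08 = 51.84, or about 52.

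**Step 1: expected slope when the dose arms do not differ.** Take one patient at each dose value.

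- Mean dose = (0 + 2.5 + 5 + 10)/4 = 4.375.
- Sxx = 4.375² + 1.875² + 0.625² + 5.625² = 54.6875.
- Sxy for a step D = D × (−1.875 + 0.625 + 5.625) = 4.375 D.
- Expected slope = 4.375 D / 54.6875 = 0.08 D per million cells, or 0.80 D from 0 to 10 million.

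So 80% of the step appears as an apparent dose effect over the studied range. The squared correlation between dose and the implant indicator is 0.467.

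**Step 2: how often the dose test rejects.** Simulation with 100,000 data sets per row, 13 per dose value, unit SD and no dose effect among implanted patients:

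| Assumed step (SD) | Sham coded 0 | Sham excluded | Implant indicator added |
|---|---|---|---|
| 0 | 5.0% | 5% | 5% |
| 0.25 | 8.0% | 5% | 5% |
| 0.5 | 17.5% | 5% | 5% |
| 0.8 | 36% | 5% | 5% |
| 1.0 | 51% | 5% | 5% |
| 1.5 | 83% | 5% | 5% |

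With 12 per dose value, the sham-coded-0 column reads 48% at 1 SD and 80% at 1.5 SD.

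**Step 3: what excluding sham costs.** With 13 per dose value:

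- Dose sum of squares with sham: 13 × 54.6875 = 711.
- Without sham, the mean dose is 5.833 and the sum of squares is 13 × (3.333² + 0.833² + 4.167²) = 13 × 29.167 = 379, a fall of 47%.
- Slope standard error ratio = √(711/379) = 1.37.

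If the response really is linear through zero, at an assumed 0.08, 0.10 or 0.12 SD per million cells, power falls from 55%, 74% and 88% to 33%, 47% and 62%. The implant indicator costs about the same, because sham then gets its own mean and the slope again rests on the 379.

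**The case against.** **Zero coding is a common convention, and the protocol uses it.** Protocol section 18.2.2.2 states the same rule. The coding in 7.2 therefore looks like a carry-over, not an invention. That explains it but does not justify it. The protocol rule covers the primary and secondary endpoints, and section 18.2.2.3 leaves exploratory analyses to the SAP. The main SAP (3.5) dropped the zero coding, and control is also left out in the Japanese supplement and the genotyping, antibody and leg activity plans. The convention suits a control that is the same procedure without the active ingredient, which this sham is not.

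**The reader will see the other results.** The per-dose one-sample tests and the pooled comparison could reveal a flat pattern across doses with sham set apart. This stands as a mitigation. It does not correct the dose p-value that will be presented.

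**Excluding sham loses information.** This also stands. Counting 39 patients instead of 52 understates the loss, as Step 3 shows.

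**Stronger readings the documents do not support.** A reader might infer that a significant dose slope is to be expected even if the doses are identical. That needs an assumed step of about 1 SD or more, and at 0.25 SD the test rejects only 8% of the time. A reader might also infer that the slope would reflect the needle alone. The step also contains the injection and any cell effect already flat at the lowest dose, and this design cannot separate them.

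**Conclusion.** The zero-coded slope in section 7.2 does not isolate dose response. It is biased by 0.08 × the sham-to-implant step per million cells, whatever causes the step. The bias follows exactly from the dose values and equal allocation. How often it produces a significant result depends on a step size that the documents do not give: about 8% to 83% over assumed steps of 0.25 to 1.5 SD, against the nominal 5%.

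The reach is limited. The MRI variables are exploratory and carry no multiplicity control. The integrated list of report tables shows one table of this kind for MRI variables (14.2.27.2). The primary FMMS comparison and its dose-response analysis do not use this coding.

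**What to change.** In Appendix E, section 7.2, exclude control from the dose regression, matching sections 7.1 and 8.0, or keep control and add an implant-versus-sham indicator beside dose. Base the dose-response conclusion on that slope. If the zero-coded slope is kept because it was prespecified, label it in table 14.2.27.2 as mixing implantation with dose.

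Keep the pooled SB623-versus-sham t-test, described as implantation plus cells against sham, since it does not isolate the procedure.

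The change is one of SAP wording and one extra model per variable. Its statistical cost is a slope standard error about 37% larger, and so lower power if the response is truly linear through zero. There is also a timing point. The integrated SAP is dated September 2019, and the main-study addendum reports analyses added after the interim results were unblinded. A control-excluded slope introduced at that stage should be marked as added and shown next to the prespecified one.
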